5.2. PRIMARY AND SECONDARY DATA ANALYSES

In primary and secondary data analyses, all stated hypotheses will be included.

In all analyses an error probability of $\alpha = .05$ will be set a priori for all interference statistics calculations. In addition to statistical significance, descriptive statistics and effect sizes will be reported. Publication of results will follow CONSORT guidelines for transparent reporting of randomized trials.

Cronbach's α and McDonald's ω will be calculated as measure of reliability of the respective questionnaires. Before data analysis assumptions of statistical methods (e.g., variance of homogeneity, normal distribution) will be tested with suitable procedures (e.g., Levene-tests, Box's M, histograms, QQ-plots, and Shapiro-Wilk-Test).

Zero-order correlations between study variables will be reported. Non-parametric correlation calculation will be based on results of (non-)normality, etc.

Variables will be standardized where applicable.

The analysis plan for H1 to H11 is as follows:

- Differences between study groups in primary and secondary outcomes before (t_0) and after the intervention (t_2) and at the time of the first follow-up (t_3) will be examined using mixed analyses of covariance (ANCOVA), with group (intervention vs. waitlist-control) as a between-subjects factor, time (t_0, t_2, t_3) as a within-subjects factor and pre-measurement (t_0) included as a covariate to increase test power. Primary outcome will be resilience (measured with SR Score) and the secondary outcomes will be resilience (measured with BRS), perceived stress, optimism, mindfulness, meaningfulness, acceptance, self-compassion, mental health, depression, and anxiety, respectively.
- If applicable, post-hoc analyses (e.g., t-tests) will be conducted.
- Effect sizes will be calculated.
- In cases of multiple testing, α will be adjusted accordingly.

The analysis plan for H12 is as follows:

- The long-term effect over the follow-up measurements (t_0 to t_5) within the intervention group will be tested using a repeated measures ANOVA.
- If applicable, post-hoc t-test or planned contrasts will be conducted.
- Effect sizes will be calculated.
- In cases of multiple testing, α will be adjusted accordingly.

If assumptions for AN(C)OVAs are violated, appropriate statistical methods will be conducted.

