2.5. SAMPLE SIZE

Previous studies from our research groups have shown a medium to large effect size for the stressor reactivity score as a primary outcome measure in online intervention studies for resilience (AG [name], unpublished). Because a large effect size was found only in a particularly stressed population, which is not expected in the sample addressed here, we assume a medium effect here (Hedges' $g = .50$). Therefore, the sample size design was calculated with a medium effect size, a significance level of 0.05 and a power of 0.90 using G*Power (Faul et al., 2007). This results in a required sample size of $n = 74$ per group ($N = 146$). As there are high dropout rates for online interventions (van Ballegooijen et al., 2014) we decided to recruit $n = 120$ individuals per group. This number is based on an assumed dropout rate of 40%.

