4.4. Hypotheses

1. The intervention will significantly increase resilience, measured with the SR Score, in the intervention group (IG) compared with a waitlist control (WLC) group at t_2 and t_3 compared to t_0 .
2. The intervention will significantly increase resilience, measured with the Brief Resilience Scale, in the intervention group (IG) compared with a waitlist control (WLC) group at t_2 and t_3 compared to t_0 .
3. The intervention will significantly reduce the perceived stress in the intervention group (IG) compared with a waitlist control (WLC) group at t_2 and t_3 compared to t_0 .
4. The intervention will significantly increase the optimism in the intervention group (IG) compared with a waitlist control (WLC) group at t_2 and t_3 compared to t_0 .
5. The intervention will significantly increase the mindfulness in the intervention group (IG) compared with a waitlist control (WLC) group at t_2 and t_3 compared to t_0 .
6. The intervention will significantly increase the meaningfulness in the intervention group (IG) compared with a waitlist control (WLC) group at t_2 and t_3 compared to t_0 .
7. The intervention will significantly increase the acceptance in the intervention group (IG) compared with a waitlist control (WLC) group at t_2 and t_3 compared to t_0 .
8. The intervention will significantly increase the self-compassion in the intervention group (IG) compared with a waitlist control (WLC) group at t_2 and t_3 compared to t_0 .
9. The intervention will significantly increase the mental health in the intervention group (IG) compared with a waitlist control (WLC) group at t_2 and t_3 compared to t_0 .
10. The intervention will significantly reduce depressive symptoms in the intervention group (IG) compared with a waitlist control (WLC) group at t_2 and t_3 compared to t_0 .
11. The intervention will significantly reduce anxiety in the intervention group (IG) compared with a waitlist control (WLC) group at t_2 and t_3 compared to t_0 .
12. In the intervention group, the intervention will lead to improved resilience by the end of the intervention (at t_2) and these improvements should be maintained at the respective follow-ups (at t_3 , t_4 , t_5 ; probably to a lesser degree).

Further longitudinal effects, intervention effects at intermediate measurements (t_1), other resilience-related outcomes, moderator and mediator analyses will be examined exploratorily. Therefore, no specific hypotheses are stated.

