5. STATISTICAL METHODOLOGY

5.1. GENERAL METHODOLOGY

Demographics will be reported with a mean and standard deviation in continuous variables (e.g., age) and with frequency and percentage in categorical variables (e.g., sex).

Items of questionnaires will be recoded (if applicable) and a scale mean or sum score will be calculated in data processing. Mean/ Sum score and standard deviation will be reported separately by treatment group.

If applicable, mean, and standard deviation of user statistics will be calculated and reported (e.g., module completion).

T-Tests for independent samples and χ^2 -tests will be used to examine whether training groups differ in demographic data or measured variables at baseline.

HANDLING OF MISSING DATA

- On the one hand, the data will be analysed according to the "intention-to-treat" principle, with missing values being replaced using appropriate imputation procedures.
- On the other hand, the results are examined in a "per-protocol" analysis, in which only those cases are considered that have gone through the complete study protocol as predicted. We include those subjects who completed the respective content lessons (excluding the introductory and final modules) addressed in the analyses/ hypotheses. To control for influences of usage, usage of intervention will be included as a covariate in an exploratory analysis.

CLASSIFICATION OF PROTOCOL VIOLATION

Exclusion of participants due to protocol violations will be reported in the methods/ results section. To examine outliers in the questionnaire data, boxplots will be created.

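### The H1–H11 model uses t0 both as an outcome level and as the covariate, and names neither the tested term nor the form of the t0 slope, so the same text supports different estimates, p values and power

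*SAP*

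**What the plan says.** SAP section 5.2 gives one model for H1 to H11: "mixed analyses of covariance (ANCOVA), with group (intervention vs. waitlist-control) as a between-subjects factor", with "time (t_0, t_2, t_3) as a within-subjects factor and pre-measurement (t_0) included as a covariate to increase test power". It names no main effect or interaction as the test and does not state the form of the covariate slope. Follow-up tests are left to be done if applicable, with t-tests as the example.

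Section 4.4 words each of these hypotheses as intervention group "compared with a waitlist control (WLC) group at t_2 and t_3 compared to t_0", which points to group × time without naming a model term.

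On estimates, section 5.2 says "In addition to statistical significance, descriptive statistics and effect sizes will be reported" and "Variables will be standardized where applicable", without saying which effect size or which SD.

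Section 2.5 plans on Hedges' g = 0.50 with "a significance level of 0.05 and a power of 0.90", and recruits 120 per group to allow for 40% dropout. Section 5.1 has the intention-to-treat analysis run with "missing values being replaced using appropriate imputation procedures".

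**The concern.** A baseline score can serve as a covariate or as one of the repeated outcomes. When it is both, the effect of the adjustment depends on choices that section 5.2 leaves open:

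1. **Group × time, common t0 slope.** t0 is constant within a person, so it drops out of every within-person contrast. The power gain given as the reason for the covariate does not occur.
2. **Group × time, with t0 × time.** Each visit has its own slope, and the adjustment works as intended.
3. **Group main effect.** The average over three visits includes t0, where the groups cannot differ after adjustment for t0 itself. The raw effect is diluted.

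This is the only model given for the primary outcome and ten secondary outcomes. Two analysts following it faithfully could report different effects and p values for H1.

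**Working it through.** **Inputs.** From the SAP: effect 0.50, alpha 0.05, target power 0.90, 120 per arm and 40% dropout, so 120 × 0.6 = 72 completers per arm. Assumed: two-sided testing, SD 1, the same effect at t2 and t3, and equal correlation ρ among t0, t2 and t3. The SAP gives no ρ; 0.3 to 0.7 is shown.

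**The plan's own figure.** Section 2.5 states 74 per group (N = 146). This was not reproduced: a two-sided t-test needs 86 per group and a one-sided one 70, and 2 × 74 = 148. Nothing below relies on it.

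**Algebra.** Let d2 and d3 be the group differences at t2 and t3 adjusted for t0.

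- *Main effect.* The adjusted difference at t0 is 0, so the estimate is (0 + d2 + d3)/3. The mean effect is (d2 + d3)/2, so the ratio is 2/3. The standard error shrinks by the same factor and t is unchanged. At ρ = 0.5 the SE without t0 in the time factor is √(0.50 × 2/72) = 0.118, and with it 0.118 × 2/3 = 0.079. The effects are 0.50 and 0.33.
- *Group × time, common slope.* Each contrast is (t2 − t0) or (t3 − t0), and the t0 term subtracts out. With n per arm, the noncentrality is λ = (n/2) × 0.5/[3(1 − ρ)].
- *Group × time with t0 × time, multivariate test.* This is ANCOVA of (t2, t3) on t0, with λ = (n/2) × 0.5/[(1 − ρ)(1 + 2ρ)].

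At ρ = 0.5 and n = 72, λ is 36 × 0.5/1.5 = 12 for the common slope and 36 × 0.5/1.0 = 18 for the adjusted test. The ratio of the two is 3/(1 + 2ρ): 1.88, 1.50 and 1.25 at ρ = 0.3, 0.5 and 0.7.

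**Power of the 2-df multivariate test** (noncentral F):

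| ρ | Common slope, 72 per arm | t0 × time, 72 per arm | n per arm for 0.90: common slope | n per arm for 0.90: t0 × time |
|---|---|---|---|---|
| 0.3 | 0.739 | 0.952 | 108 | 59 |
| 0.5 | 0.876 | 0.971 | 78 | 53 |
| 0.7 | 0.983 | 0.996 | 48 | 39 |

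Simulation (10,000 trials per scenario) gave 0.735, 0.876 and 0.986 for the common slope, and 0.950, 0.970 and 0.997 for t0 × time. The univariate version of the t0 × time test gave 0.897, 0.952 and 0.996. If all 120 per arm contributed full data, which is an upper bound because imputed values carry less information, the noncentral-F figures are 0.930 against 0.998 at ρ = 0.3 and 0.984 against 0.999 at ρ = 0.5.

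**Checks on simulated data.**

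- In one data set the main effect was 0.382 (SE 0.068) with t0 in the time factor and 0.573 (SE 0.101) without, with t = 5.65 in both.
- In the same data set the common-slope contrasts were 0.509 and 0.644, both with SE 0.1465, whether or not the covariate was included. The multivariate F was 10.57 for the common slope, 15.84 with t0 × time, and 15.84 for ANCOVA of t2 and t3 on t0.
- In a second data set the contrasts themselves differed: 0.389 and 0.525 with the common slope, 0.412 and 0.549 with t0 × time. There the main effect with and without t0 in the time factor was 0.293 against 0.440 in baseline-SD units, but 0.777 in both when divided by the model's residual SD.

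**Under the null** (ρ = 0.5), rejection rates were 0.049 to 0.055 for all tests.

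**The case against.** The best case for the plan is that its text leans towards the sound fit. The hypotheses point to group × time, so the diluted main effect is the least likely choice, and even then t, p and partial eta squared are unaffected. The stated aim of gaining power makes sense only if the slope differs by time. Listing Box's M suggests a multivariate formulation, in which each visit has its own coefficient. The power loss also rests on an unstated correlation: at ρ = 0.6 the common-slope test has power 0.94 with 72 per arm, and at 0.8 it has 0.999 against 1.00. Part of any shortfall from 0.90 belongs to the sample size, since a plain two-sided t-test with 72 per arm has power of only 0.846.

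Much of this is fair. The loss is conditional, and the main-effect fit does harm only if a raw difference, or one scaled by a raw SD, is reported. No loss is exact only for the multivariate test and the per-visit contrasts; the univariate form falls just under 0.90 at ρ = 0.3 (0.897 in the simulation above, 0.888 with a Greenhouse–Geisser correction in a separate one).

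But these cues do not settle the model. No t0 × time term is written, and the primary analysis should not depend on a software default. The sample size does not explain the gap between the two slopes either, because both were compared at the same 72 per arm.

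**Conclusion.** The concern holds. Section 5.2 gives t0 two roles and leaves open the two choices that decide what the adjustment does; nothing else in the SAP closes them. With a common slope, the covariate does nothing for the term that section 4.4 suggests. At 72 per arm and effect 0.50, the cost is about 21 percentage points of power at ρ = 0.3, 9 or 10 at ρ = 0.5 and 1 at ρ = 0.7, and the test misses the planned 0.90 at the first two. With the main effect, a raw or raw-SD-scaled estimate is a third too small. With t0 × time and the multivariate test there is no harm. False positives are not the issue. The power figures rest on the assumed ρ, equal effects at both visits and complete data on 72 per arm; the cancellation and the two-thirds ratio rest on none of these.

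**What to change.** Give t0 one role in section 5.2. Either of these will do:

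- Take t0 out of the time factor and model t2 and t3 with group, time, group × time, t0 and t0 × time.
- Keep t0 as an outcome level with baseline means constrained equal across arms, and drop the covariate.

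The smallest edit would be to keep the present layout, add t0 × time and name the multivariate group × time test; this gives the same multivariate result, but t0 keeps its double role.

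State which group test decides H1 to H11. The joint test of the differences at t2 and t3, or the test of their average, is the sponsor's choice, as neither is uniformly better. Report the adjusted differences at t2 and at t3 separately, and name the SD behind any standardised effect.

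The cost is SAP wording and analysis code. No new data or participants are needed.

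### The test at t2 and at t3 for H1–H11 is left open, and the only example named, the t-test, would lose or underuse the baseline adjustment that the plan adds for power.

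*SAP*

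**What the plan says.** SAP section 4.4 words each of H1 to H11 as a change in the intervention group "compared with a waitlist control (WLC) group at t_2 and t_3 compared to t_0". Each hypothesis therefore covers two visits.

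SAP section 5.2 analyses H1–H11 with a mixed ANCOVA. Group is the between-subjects factor, the model has "time (t_0, t_2, t_3) as a within-subjects factor", and it has "pre-measurement (t_0) included as a covariate to increase test power". The provision for follow-up tests is "If applicable, post-hoc analyses (e.g., t-tests) will be conducted". Alpha is to be adjusted where there is multiple testing, but no method is named.

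For H12, the within-group question, the parallel line in the same section reads "If applicable, post-hoc t-test or planned contrasts will be conducted". Contrasts are thus named for H12 and not for the randomised comparison.

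**The concern.** A mixed model over several visits yields terms for group, time and their interaction. A significant term does not by itself say whether the arms differ at t2, at t3 or at both. Those statements, which most readers will look for, need a further step, and the plan leaves that step to a choice made later.

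The one example given does not fit the plan's own reasoning. The t0 score is in the model to gain power, but an ordinary t-test carries no covariate. On raw scores it discards t0 and keeps any chance baseline imbalance. On change scores it uses t0, but less efficiently than regression adjustment. The visit-level results could then be less precise than the plan intends, and could disagree with the adjusted model in the same report. The trial is unblinded (SAP section 2.2), which is a further reason to settle the choice before the data are seen.

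**Working it through.** **Inputs from SAP section 2.5.** Effect size g = .50; "a significance level of 0.05 and a power of 0.90 using G*Power"; 120 recruited per group; 40% dropout assumed. Analysable per arm: 120 × (1 − .40) = 72.

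**Assumptions not in the SAP.** Two-sided testing. Correlation r between t0 and the later score of .3 to .7. Where two visits share alpha, .05/2 = .025 each, as an illustration.

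**The plan's own figure.** The SAP gives 74 per group with a total of 146 (2 × 74 is 148). For d = .50, alpha .05 and power .90, a one-sided t-test needs 70 per group and a two-sided t-test 86. A one-sided Wilcoxon–Mann–Whitney test with asymptotic relative efficiency 3/π needs 73 per group, total 146, with power .902. That variant matches the stated total, although the SAP does not name the test. It is an unadjusted two-group comparison, so on this reading the sample size does not rely on the covariate.

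**Power at one visit, n = 72 per arm (noncentral t).** The noncentrality is the standardised effect × √(n/2), and √(72/2) = 6.

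- Raw t-test: effect .50, noncentrality .50 × 6 = 3.00, 142 df.
- t0-adjusted contrast: the residual variance is (1 − r²) times the raw variance, so the effect is .50/√(1 − r²), with 141 df. For r = .3, .5 and .7 the noncentrality is 3.14, 3.46 and 4.20.
- Change-score t-test: the variance is 2(1 − r) times the raw variance, so the effect is .50/√(2(1 − r)), with 142 df. The noncentrality is 2.54, 3.00 and 3.87.

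| Test | alpha | r = .3 | r = .5 | r = .7 |
|---|---|---|---|---|
| Raw t-test | .05 | .846 | .846 | .846 |
| Change-score t-test | .05 | .712 | .846 | .970 |
| t0-adjusted contrast | .05 | .878 | .931 | .987 |
| Raw t-test | .025 | .768 | .768 | .768 |
| Change-score t-test | .025 | .607 | .768 | .945 |
| t0-adjusted contrast | .025 | .809 | .883 | .973 |

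The adjusted contrast gains 3, 8 and 14 points over the raw t-test at .05, and 4, 12 and 20 points at .025. The change-score test is weaker than the adjusted contrast at each r shown, and at r = .3 it is weaker than the raw test. A simulation of 20,000 trials per r agreed: raw .844 to .846; adjusted .875, .932 and .985.

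**Disagreement between the two tests.** In 20,000 simulated trials per r, the raw t-test was non-significant in about 5% (r = .3), 10% (r = .5) and 12% (r = .6) of trials with a significant adjusted result. The reverse conflict occurred in about 0.5 to 1.6% of all trials.

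**The case against.** The strongest reply is that the plan commits to nothing wrong. The follow-up line is conditional and gives t-tests only as an example. Adjusted contrasts are not excluded, and a change-score test would match the comparison with t0 in the hypotheses. This stands. A reader might infer that the plan prescribes plain unadjusted t-tests, but the text does not say so. The gap is one of specification.

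Second, the ANCOVA is the named analysis of H1–H11. A reader might infer that the t-tests decide the hypotheses at t2 and t3. The SAP does not say that either; it does not state which term or test settles each visit.

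Third, a reader might fear paired tests within each arm, where significance in one arm only would be taken as a group effect. Nothing in the plan for H1–H11 mentions within-arm tests, the hypotheses are worded between groups, and within-group analysis belongs to H12. The SAP also gives no figure for drift over time, so no rate of false claims can be attached to that reading.

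Fourth, an independent t-test after randomisation is valid, and the SAP does not state sidedness. At one-sided .05 the raw t-test with 72 per arm has power .91, above the planned .90. At r = .3 the two-sided gain is only 3 points. Both facts limit the size of the point. They do not remove it, because the adjusted contrast uses data already collected and is at least as powerful at every r examined.

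**Conclusion.** The point holds as a gap in specification. The plan does not fix the test at t2 and at t3 for H1–H11, and an ordinary version of its only example would work against its stated reason for including t0. With 72 per arm and g = .50, two-sided, the power forgone by a raw t-test runs from 3 points (r = .3) to 14 (r = .7) at .05, and from 4 to 20 at .025 per visit. At two-sided .05 the raw test falls short of the planned .90, and the adjusted contrast exceeds it at r = .5 and above. These figures depend on the assumed r, sidedness and alpha split.

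The consequence is lost precision and visit-level results that may disagree with the main model. The documents do not support a charge of bias or of type I error inflation.

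**What to change.** Replace the post-hoc line for H1–H11 in SAP section 5.2 with:

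> The group difference at t2 and at t3 is estimated as the t0-adjusted between-arm contrast (ANCOVA with t2 and t3 as the outcome levels and t0 as covariate, with group-by-time and t0-by-time terms), with 95% CI and the planned alpha adjustment. Unadjusted and within-arm t-tests are descriptive only and do not support H1–H11.

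It is not enough to take the contrast from the ANCOVA as now written, because t0 is there both a level of the time factor and the covariate. For this contrast, t0 has to be the covariate only.

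The change costs one sentence of SAP wording and a model definition that agrees with it. It needs no new data and no extra participants.

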5.3. EXPLORATORY DATA ANALYSES

All other outcome measures mentioned above and not directly addressed in the intervention will be evaluated exploratively.

In addition, changes will be examined in correlative network analyses of the variables. Moderator and mediator analyses are intended as exploratory analyses to examine the influence of mediating/moderating variables (e.g., gender, personality, intervention usage, attitudes toward online psychological interventions, coping styles) of the primary correlations.

The intermediate survey (t_1) will be exploratively included in the analyses.

References

<https://doi.org/10.6102/ZIS35>
- Brailovskaia, J., & Margraf, J. (2020). How to measure self-esteem with one item? Validation of the German single-item self-esteem scale (G-SISE). *Current Psychology*, *39*(6), 2192–2202.
<https://doi.org/10.1007/s12144-018-9911-x>
- Breyer, B., & Bluemke, M. (2016). Deutsche Version der Positive and Negative Affect Schedule PANAS (GESIS Panel). *Zusammenstellung sozialwissenschaftlicher Items und Skalen (ZIS)*.
<https://doi.org/10.6102/ZIS242>
<https://doi.org/10.2196/14566>
<https://doi.org/10.1371/journal.pone.0192761>
